2.1 Overview

2.1.1 Primary Objectives

To evaluate the effectiveness of collaborative care for opioid use disorder (OUD) and co-occurring depression or PTSD (CC-COD) on patient initiation of medications for OUD (MOUD), quality of care for OUD, depression symptoms, and PTSD symptoms relative to enhanced usual care (EUC).

2.1.2 Secondary Objectives

To test mediators (patient experiences with care and working alliance with the Care Coordinator) of treatment quality and patient-reported outcomes and, in exploratory analyses, test moderators of access, quality, and outcomes compared with patients assigned to EUC.

2.1.3 Patient population

The study population is patients ≥ 18 years of age attending one of 18 primary care clinics in five large healthcare organizations (First Choice Community Healthcare, Providence St. John's Primary Care, Hidalgo Medical Services, University of New Mexico and Los Angeles County Department of Healthcare Services) in New Mexico and California who have probable OUD and either depression or PTSD. Both patients enrolled in the parent study (CLARO) and the CR (CLARO+) are included.

2.1.4 Inclusion/exclusion criteria

Patients will be eligible to participate in the study if they meet the following inclusion criteria:

- Consider this clinic to be their usual source of care
- Age 18 or older
- Probable OUD diagnosis
- Probable PTSD or major depression diagnosis
- Speak and understand English or Spanish
- Have capacity to give informed consent
- Provide a signed and dated informed consent form.

Pregnant women will not be excluded.

Patient participants will not be eligible to participate in the study if they meet the following exclusion criterion:

- The patient requires immediate medical (emergency procedure needed) or psychiatric intervention (i.e., self-injured, active psychosis).

2.2 Blinding

The research staff will be blind to the treatment assignment and participant outcomes until database lock, except for research assistants at the point of randomization. All aspects of this analysis plan were finalized prior to unblinding. Clinic staff and participants will not be blind to the treatment assignment, as it is not possible to deliver the intervention with blinding.

2.3 Definitions of study arms

CC-COD intervention. The intervention is based on a service delivery approach that uses multi-faceted interventions to improve access and quality of care. It is based on Wagner's Chronic Care Model and subsequent modifications. Care coordinators use Motivational Interviewing and meet with patients individually for at least 13 visits over six months. In the first two months, the Care Coordinator meets weekly with the patient. In month three, meetings are biweekly. In months four through six, the Care Coordinator and the patient meet once a month. Meetings can be in-person or by phone, and ideally occur in-person prior to an appointment with the patients' primary care provider (PCP) so that the Care Coordinator can relay information (e.g., symptoms, insights regarding barriers to care) to the PCP before the appointment with the patient. Meetings can also be conducted more frequently or for longer than six months should the care team decide it is best for the patient. The first meeting between the Care Coordinator and the patient occurs in a care initiation visit, where the Care Coordinator develops patient trust and engagement, assesses various patient domains, discusses the conditions to target, links the patient to care, and coordinates linkages with the PCP and BHP. Assessment includes asking the patient about substance use severity using the PROMIS-7, depression symptoms using the PHQ-9, PTSD symptoms using the PCL-5, along with the WellRX to assess social needs, PEG Pain Monitor, and social support measures. The Care Coordinator then collaborates with the patient using MI to assess treatment experiences and

barriers to care, provides information about treatment options, and then coordinates next steps with the patient. After the care initiation visit, the Care Coordinators meets with the patient in monitoring visits for the remainder of the six-month intervention period. Care monitoring visits focus on engagement, assessment, and linkages. Five opioid use questions are asked at each visit, whereas the PROMIS-7, PCL-5, and PHQ-9 are administered monthly. In this care model, the Care Coordinator is supported by a behavioral health consultant (BHC) and a Care Coordinator supervisor with expertise in supervising community health workers. The Care Coordinator, BHC, and Care Coordinator supervisor meet weekly to discuss the Care Coordinator's caseload. Throughout the study period, the Care Coordinator enters patient information into a clinical registry, a patient caseload tool with four main purposes: (1) track population-level outcomes and engagement, (2) prompt the Care Coordinator with reminders and alerts to ensure accountable outreach when a patient has an upcoming appointment or needs a higher-level of care, (3) prompt treatment-to-target by showing trends in patient symptom severity scores and flags the Care Coordinator when to consult with the BHC, and (4) facilitate caseload review between the Care Coordinator, BHC, and Care Coordinator supervisor through caseload-level reports that display patient-level ID numbers of those who should be discussed.

Enhanced Usual Care (EUC) intervention. EUC includes both the evidenced-based psychotherapy (i.e., Problem Solving Therapy for depression and Written Exposure Therapy for PTSD) and pharmacotherapy (i.e., MOUD and psychotropic medications for MDD/PTSD) provided in CC-COD, but the primary difference is the absence of a care management team and a clinical registry to coordinate care with the patients in EUC.

2.4 Competitive Revision

On 6/6/2022, approximately 5 months after we started data collection, we submitted a competitive revision (CR) which was awarded 8/31/2022. The CR uses the same patient population and inclusion/exclusion criteria as the original study and introduced a new study arm, where patients received up to 3 additional clinical components: support person education, Naloxone training, and Caring Contacts. We refer to this modified intervention as CC-COD+ and the modified study as CLARO+.

2.5 Definitions of outcomes

2.5.1 Primary outcomes

Table 1 defines the primary outcomes of this study. The hypotheses associated with these outcomes are as follows:

1. We hypothesize that patients with a new OUD episode of care who are randomized to CC-COD/CC-COD+ will receive buprenorphine within fewer days after that care episode

than new OUD patients who are randomized to enhanced usual care. Alternatively, the null hypothesis is that there will be no difference in the number of days until receipt of buprenorphine with a new OUD episode of care.

2. We hypothesize that patients who are randomized to CC-COD/CC-COD+ will have more days of buprenorphine treatment within 180 days of study enrollment than patients who are randomized to enhanced usual care. Alternatively, the null hypothesis is that there will be no difference in the number of days of cumulative buprenorphine treatment within 180 days of study enrollment.
3. We hypothesize that, among patients with probable depression at study enrollment, those who are randomized to CC-COD/CC-COD+ will have a greater reduction in depression symptoms 6 months after study enrollment compared to those who are randomized to enhanced usual care. Alternatively, the null hypothesis is that there will be no difference in depression symptoms 6 months after study enrollment among those with probable depression at enrollment.
4. We hypothesize that, among patients with probable PTSD at study enrollment, those who are randomized to CC-COD/CC-COD+ will have a greater reduction in PTSD symptoms 6 months after study enrollment compared to those who are randomized to enhanced usual care. Alternatively, the null hypothesis is that there will be no difference in PTSD symptoms 6 months after study enrollment among those with probable PTSD at enrollment.

A union-intersection test will be used to test the overall success of the study that combines the four primary outcomes into a single composite hypothesis. In particular, the null hypothesis is the intersection of the four primary outcome null hypotheses (i.e., all null hypotheses are true), and the alternative is the union of the alternative hypotheses (i.e., at least one alternative hypothesis is true). As described in subsequent sections, either a Bonferroni or Benjamini-Hochberg correction on the individual hypotheses will be used to control the error rate of this composite test.

Table 1: Definition of primary outcomes

Outcome	Population ^a	Definition	Measure Scale	Source
Buprenorphine access	Study participants with a new episode of OUD care (no care for at least 30 days prior)	Number of days until first buprenorphine prescription after study enrollment	Time-to-event	Survey, PMP
Buprenorphine continuity of care	Study participants not on methadone at baseline	The cumulative number of days the patient receives buprenorphine during the 180 days after study enrollment.	Continuous	Survey, PMP
MDD symptom severity	Study participants with probable MDD at baseline (PHQ-8 \geq 10)	PHQ-9 at 6 months	Sum of items (0-27)	Survey
PTSD symptom severity	Study participants with probable PTSD at baseline (PC-PTSD-5 \geq 3)	PCL-5 at 6 months	Sum of items (0-80)	Survey

^a Study participants means all study participants who consented and were randomized to the intervention or to EUC.

2.5.2 Secondary outcomes

There are 13 pre-specified secondary outcomes, which are described in

Table 2. After drafting of the initial SAP, but prior to analyzing outcomes and breaking the blind, some secondary outcomes were modified, cut, or reclassified as exploratory, as detailed in the revision table in section 1.2.

Table 2: Definition of secondary outcomes

Outcome	Population ^b	Definition	Measure Scale	Source
Mental Health				
Access to MDD and/or PTSD treatment	Study participants who did not have any visits (behavioral health treatment or medication) for MDD and/or PTSD in 30 days prior to study enrollment	Receipt of medication and/or behavioral treatment associated with an MDD or PTSD diagnosis within 30 days of study enrollment (initial) or within 180 days of study enrollment (any)	Binary	EMR, Survey
Quality of care for MDD	Study participants with probable MDD at baseline (PHQ-8 ≥ 10) and a new episode of MDD care (no MDD care for at least 30 days prior to enrollment)	Four psychotherapy visits in the first six months or an adequate (60 day) medication trial for new episodes of MDD care (completed within 6 months)	Binary	EMR, Survey
Quality of care for PTSD	Study participants with probable PTSD at baseline (PC-PTSD-5 ≥ 3) and a new episode of PTSD care (no PTSD care for at least 30 days prior to enrollment)	Four psychotherapy visits in the first six months or an adequate (60 days) medication trial for new episodes of PTSD care (completed within 6 months)	Binary	EMR, Survey
MDD remission	Study participants with probable MDD at baseline (PHQ-8 ≥ 10)	PHQ-9 < 5 at 6 months	Binary, based on sum of items (0-27)	Survey
MDD response	Study participants with probable MDD at baseline (PHQ-8 ≥ 10)	PHQ-9 score at 6 months less than 50% of baseline score	Binary, based on sum of items (0-27)	Survey

PTSD remission	Study participants with probable PTSD at baseline (PC-PTSD-5 \geq 3)	PCL-5 < 34 at 6 months	Binary, based on sum of items (0-80)	Survey
PTSD response	Study participants with probable PTSD at baseline (PC-PTSD-5 \geq 3)	PCL-5 score at 6 months less than 50% of baseline score	Binary, based on sum of items (0-80)	Survey
Active suicidal ideation	All study participants	Dichotomized Columbia Suicide Severity Rating Scale at 6 months: answer YES to Question 3, 4, and/or 5 and/or YES to Question 7	Binary	Survey
Substance Use				
Opioid use frequency	All study participants	Days of opioid use in the past 30 days from NSDUH	Total days of opioids use (0-30)	Survey
Opioid overdose events	All study participants	Opioid overdose events in the previous three months	Binary, at least 1 event	Survey
Overall Health				
Physical health functioning	All study participants	Veterans RAND 12-item Health Survey (VR-12) – physical health subscale	MEPS ¹ standard	Survey
Mental health functioning	All study participants	Veterans RAND 12-item Health Survey (VR-12) – mental health subscale	MEPS standard	Survey

^b Study participants means all study participants who consented and were randomized to the intervention or to EUC.

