	
Quality of care for MDD:¹³ 4 psychotherapy visits in the first 6 months or an adequate (60 day) medication trial for a new episode of MDD care (no MDD care for at least 30 days prior to enrollment)
 
Quality of care for PTSD:¹³ 4 psychotherapy visits in the first six months or an adequate (60-day) medication trial for a new episode of PTSD care (no PTSD care for at least 30 days prior to enrollment)
 
MDD remission: PHQ-9 < 5 at 6 months, among study participants with probable MDD at baseline (PHQ-8 ≥ 10)
 
MDD response: PHQ-9 score at 6 months less than 50% of baseline score, among study participants with probable MDD at baseline (PHQ-8 ≥ 10)
 
PTSD remission: PCL-5 < 34 at 6 months, among study participants with probable PTSD at baseline (PC-PTSD-5 ≥ 3)
 
PTSD response: PCL-5 score at 6 months less than 50% of baseline score, among study participants with probable PTSD at baseline (PC-PTSD-5 ≥ 3)
 
Active suicidal ideation: Dichotomized Columbia Suicide Severity Rating Scale¹¹ at 6 months: answer YES to Question 3, 4, and/or 5 and/or YES to Question 7.
 
Substance Use
		

OBJECTIVES	ENDPOINTS	JUSTIFICATION FOR ENDPOINTS	PUTATIVE MECHANISMS OF ACTION
	
Opioid use frequency: Days of opioid use in the past 30 days, measured using SAMHSA National Survey on Drug Use and Health (NSDUH)⁶ items
 
Opioid overdose events: Opioid overdose events in the previous three months, from Naloxone Overdose Baseline Questionnaire¹⁰
 
Overall Health
 
Physical health functioning: Veterans RAND 12-item Health Survey (VR-12)¹⁴ – physical health subscale
 
Mental health functioning: Veterans RAND 12-item Health Survey (VR-12)¹⁴ – mental health subscale
		
Tertiary/Exploratory			
To evaluate the effectiveness of CC-COD compared to EUC.	
Drug use frequency: Days of use in the past 30 days for five drug categories (prescription opioids, heroin, cocaine/crack, methamphetamine/ other stimulants, and tranquilizers/sedatives), measured using SAMHSA National Survey on Drug Use and Health (NSDUH)⁶ items
 
Stimulant use frequency: Days of stimulant use in the past 30 days from NSDUH⁶
 
Alcohol use: Alcohol Use Disorder Identification Test – Consumption (AUDIT-C)⁸
		

OBJECTIVES	ENDPOINTS	JUSTIFICATION FOR ENDPOINTS	PUTATIVE MECHANISMS OF ACTION

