Note that we will not administer item 9 from the PHQ-9 ("thoughts that you would be better off dead, or of hurting yourself") during eligibility screening. This avoids asking for information that could require us to break confidentiality before a participant has completed the informed consent process. It does not affect our eligibility criteria because the 8-item and 9-item versions of the PHQ are scored identically.²⁰⁹ We will obtain a complete initial PHQ-9 score during the baseline interview in one of two ways: (1) if 3 or fewer days pass since the eligibility screener, administer PHQ item 9 during the baseline interview, then combine it with items 1-8 from the eligibility screener for scoring; or (b) if more than 3 days have passed since the eligibility screener, re-administer the full PHQ-9 during the baseline interview and use that full score for all subsequent analyses (this latter option does not affect the eligibility determination).

Patients who screen eligible will be contacted within 4 weeks to participate in the study. The research assistant (RA), who is employed by the RAND/UNM research team, will contact the participant to schedule a study visit that will consist of a screening questionnaire, the informed consent process and a baseline interview assessment. Due to COVID-19, the consent may or may not be conducted in person. We have created a contingency plan based on recommendations from institutional revisions to research procedures. If the consent process will not be conducted in person, the RA will consent the participant via an IRB approved, virtual method: verbal consent with electronic documentation of the consent process. Regardless of whether or not the consent is obtained via telephone or a video conferencing platform, this should not impact the RA's ability to move directly into the baseline assessment immediately following the consent. The participant will be notified ahead of time that they should plan on spending approximately 1 hour to complete this study visit.

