Our revised outcomes are as follows: (1) Buprenorphine continuity of care,⁴ which refers to the numbers of cumulative days the patient receives buprenorphine during the 180 days after study enrollment; (2) Buprenorphine access,⁵ defined as number of days until first buprenorphine prescription after study enrollment, among patients with a new episode of OUD care (i.e., no care for at least 30 days prior); (3) MDD symptom severity, as measured by the PHQ-9²; and (4) PTSD symptom severity, as measured by the PCL-5.¹⁷⁹ Buprenorphine continuity and access will be based on prescription (data and frequency) data from the follow-up assessments and New Mexico and California Prescription Drug Monitoring Program data. MDD and PTSD symptom severity will be collected in baseline and follow-up assessments, with primary outcome analyses based on final scores across the six-month period.

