3.4.3 Binary outcomes

Binary outcomes will be analyzed using a logistic regression model including health system, prior MOUD exposure, and treatment assignment as predictors. The logistic regression model is given by:

$$\log\left(\frac{\Pr(y_{ij} = 1)}{1 - \Pr(y_{ij} = 1)}\right) = \alpha_j + \nu P_{ij} + \beta T_{ij}$$

where α_j are health system-level fixed effects and e^β is the odds ratio for CC-COD/CC-COD+ versus EUC. The statistical hypotheses from the logistic regressions will be of the form:

$$\begin{aligned} H_0: \beta &= 0 \text{ vs} \\ H_1: \beta &\neq 0. \end{aligned}$$

The estimated effects from these models will be converted to risk differences using the recycled prediction approach to estimate marginal effects.⁴ Both odds ratios and risk differences may be reported to improve interpretation.

If necessary, outcomes that require elements from the 6-month follow-up survey may be weighted to account for nonresponse as previously described. Additionally, if we do not have sufficient sample size to support modeling P_{ij} (prior MOUD treatment), then it will be removed from a given model. We will assess this by examining a cross-frequency of P_{ij} with out outcome y_{ij} and ensure that we have at least 20 individuals per cell.

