3.5.2 Secondary outcomes

Secondary endpoints are grouped into domains of conceptually related endpoints, and the outcomes will be analyzed adjusting for multiple comparison within domain using a Bonferroni correction. Table 8 provides the grouping of the secondary outcomes into domains, along with the observed outcome distributions, the minimum detectable effect size at 80% power and a family-wise error rate of 5%, and a reference effect size (if available). The vast majority of secondary outcomes are sufficiently powered to detect clinically meaningful effects or effects found in similar interventions.

Table 9: Minimum detectable effect size for secondary outcomes

Outcome	Observed distributions	Minimum detectable effect size	Reference effect size
Mental Health			
Access to MDD and/or PTSD treatment	
 • N=259 • 65.5% access treatment 	19.2 percentage points	None
Quality of care for MDD	
 • N=210 • 8.8% with quality care 	18.9 percentage point	16 percentage points for medication adherence ¹² at 3 months
Quality of care for PTSD	
 • N=300 • 9% with quality care 	15.3 percentage point	Expect similar to MDD
MDD remission	
 • N=405 • 16.0% remission 	15.0 percentage points	15 percentage points ¹³
MDD response	
 • N=405 • 26.2% response 	15.8 percentage points	20 percentage points from CALM ¹³ or 23 percentage points from STEPS-UP ¹¹
PTSD remission	
 • N=368 • 56.2% remission 	17.8 percentage points	Similar to MDD remission
PTSD response	
 • N=365 • 21.6% response 	17.7 percentage points	18 percentage points ¹¹

Active suicidal ideation	
• N=523• 24.2% at 6-months	14.5 percentage point	Any reduction
--------------------------	---	-----------------------	---------------

Substance Use

Opioid use frequency	
• N=523• Mean (sd) = 4.3 (9.6)	0.27 standard deviations; 2.6 raw scale	None
----------------------	---	---	------

Opioid overdose events	
• N=525• 2.1% at 6-months	5.9 pct point reduction	None
------------------------	--	-------------------------	------

Overall Health

Physical health functioning	
• N=525• Mean (sd) = 36.8 (12.0)	3.2 points	Similar to mental health functioning

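### PTSD remission has no baseline PCL-5 floor, so participants below 34 at both baseline and 6 months count as remitted

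*SAP*

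**What the plan says.** SAP section 2.5.2, Table 2, gives the outcome as "PCL-5 < 34 at 6 months" in participants with probable PTSD at baseline. The protocol's section 3 has the same rule: "PTSD remission: PCL-5 < 34 at 6 months, among study participants with probable PTSD at baseline (PC-PTSD-5 ≥ 3". Entry to the denominator therefore uses the short screener, and the outcome uses the PCL-5.

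The PCL-5 is available at baseline. Protocol section 8.1 states that "MDD and PTSD symptom severity will be collected in baseline and follow-up assessments", and the Schedule of Activities marks PTSD remission status at the baseline visit. The analysis does not use it for this endpoint. SAP section 3.4.3 says "Binary outcomes will be analyzed using a logistic regression model including health system, prior MOUD exposure, and treatment assignment as predictors". The only sensitivity analysis in SAP section 3.2 concerns the CC-COD population, not baseline severity.

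SAP Table 9 reports "56.2% remission" on N=368, a minimum detectable effect of "17.8 percentage points", and, for PTSD response, "21.6% response" on N=365.

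**The concern.** Remission normally means moving from above a threshold to below it. Here someone who starts at PCL-5 25 and finishes at 30 has worsened slightly and is counted as a success. Two things are at stake.

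- **Interpretation.** A rate near 56% labelled remission will be read as recovery from probable PTSD, although an unknown part of it may be people who were never above the cut-off.
- **Power.** If treatment does little for people already below 34, they add near-constant successes to both arms and shrink the risk difference. The Table 9 calculation treats all 368 as able to move from above to below.

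MDD remission is much less exposed, because entry (PHQ-8 of 10 or more) and outcome (PHQ-9 below 5) use nearly the same scale.

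**Working it through.** **Inputs from the SAP.** N=368 with 1:1 allocation, so n=184 per arm. Remission is 56.2%. Tests are two-sided with a Bonferroni correction over the eight Mental Health outcomes, so α = 0.05/8 = 0.00625 and z = 2.734. Power is 80%. The 6-month PCL-5 has mean 32.2 and SD 17.8 (section 3.5.1).

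**Input not in the documents.** The share q with baseline PCL-5 below 34. Table 7 is an empty shell.

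**Step 1: reproduce the stated figure.** Power = Φ{[d√n − z√(2p̄(1−p̄))] / √(p₁(1−p₁)+p₂(1−p₂))}. With p₁ = 0.562 as the reference-arm rate, p₂ = 0.740, d = 0.178 and p̄ = 0.651:

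(0.178 × 13.565 − 2.734 × 0.674) / 0.662 = 0.863, so power is 80.6%.

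Solving for exactly 80% gives 17.7 points. The plan's 17.8 is reproduced. (Taking 56.2% as the overall rate instead gives 18.4.)

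**Step 2: how many might start below 34?** Assume normal baseline scores, so q = Φ((34 − mean)/SD).

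- Mean 38, SD 17: Φ(−0.235) = 41%.
- Mean 48, SD 15: Φ(−0.933) = 18%.
- Means of 40-45 with SD 15-17: 23-36%.

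**Step 3: effect needed among those who start at or above 34.** Assume no treatment effect in those starting below.

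- Pooled endpoint: 17.7/(1−q).
- Restricted analysis: n = 184(1−q) per arm and reference rate r = (0.562 − q·s)/(1−q), where s is the share of low starters still below 34 at 6 months (taken as 80-100%). Solve the Step 1 formula for 80% power.

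| q | r | Pooled endpoint needs | Restricted analysis needs |
|---|---|---|---|
| 10% | 51-54% | 19.7 points | about 19 |
| 20% | 45-50% | 22.1 | about 20.5 |
| 30% | 37-46% | 25.3 | about 22 |
| 40% | 27-40% | 29.5 | 23-24 |

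Under this assumption the restricted analysis needs the smaller effect at every share, despite its smaller N.

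**Step 4: what the SAP's own rates show.** 56.2 − 21.6 = 34.6, so roughly 34-35% of the group finished below 34 without falling below half their baseline score. For MDD the order is reversed (16.0% remission, 26.2% response). The PTSD pattern is what a sizeable low-starting group would produce. It is also what falls from moderate baselines produce: a 6-month score of at most 33 without response is possible from any baseline up to 2 × 33 = 66.

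**The case against.** Several points on the other side stand.

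- **The rates do not prove the mechanism.** A reader might infer from 56.2% against 21.6% that a third of the group started below the cut-off. The documents do not support that: any baseline from 34 to 66 can give remission without response (60 to 32, for example).
- **Low starters are not people who cannot contribute.** The endpoint is status at 6 months. In a bivariate normal model with baseline mean 40-45, SD 15-17 and correlation 0.5-0.65, 12-25% of those starting below 34 finish at or above it. Treatment that prevents worsening would count, so the Step 3 dilution is the case of no effect at all in that group.
- **MDD remission is not strictly immune.** Protocol section 8.1 says "Patients who screen eligible will be contacted within 4 weeks to participate in the study", and a PHQ-9 re-administered more than 3 days after screening replaces the screening score in later analyses without changing eligibility. A baseline PHQ-9 below 5 is unlikely but not ruled out.
- **The power gain is modest.** At q = 30% the requirement falls from about 25 to about 22 points. Table 9 likens the reference effect to that for MDD remission, listed as 15 points. Both versions miss it, as does 17.8.
- **Other endpoints cover PTSD.** The primary endpoint is continuous PCL-5, and response is relative to each participant's own baseline. Neither depends on this cut-off.
- **Timing.** Pooled outcome rates have been seen, and SAP section 2.2 says the plan was final before unblinding. Changing the main population now is not free of cost.

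These points limit the size of the problem and shape the remedy. None supplies a baseline condition, so the definitional point remains.

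**Conclusion.** The definition, as written, counts people below 34 at both times as remitted, and nothing elsewhere in the two documents corrects this. That much is certain from the text. A reader might go further and infer a biased arm comparison. That does not follow, because the same rule applies to both randomised arms. The consequences are a misleading label and a probable loss of power for one of eight Mental Health secondary outcomes.

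The size is not known. A share of 18-41% starting below 34 rests on an assumed baseline mean of 38-48 and SD of 15-17. The 25 against 22 points further assumes a 30% share and no treatment effect among low starters; with some protective effect in that group, the dilution is smaller.

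**What to change.** 1. Add baseline PCL-5 as a covariate in the PTSD remission model. This improves precision but does not cure the labelling, since people never above 34 would still count as remitted.
2. Analyse remission among participants with PC-PTSD-5 of 3 or more and baseline PCL-5 of 34 or more. If the blind is intact, make this the main definition in Table 2 and keep the present one as a sensitivity analysis. If not, keep the present definition as main and add the restricted one as a labelled sensitivity analysis. Baseline interviews precede randomisation, so the restricted comparison is still a randomised one.
3. Report the share below 34 at baseline by arm, and restate the Table 9 row for the restricted N.

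The cost is SAP wording and one re-run. No new data are needed: PTSD response already uses baseline PCL-5 and has N=365 against 368. The downside is a smaller N for this row and a denominator that no longer matches the other PTSD endpoints.
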